## 4 CHANGES COMPARED TO THE PROTOCOL

This SAP contains the following changes compared to the protocol:

1. The follow up visits shall be performed 3 months post final treatment and not 4 months post final treatment as stated in the protocol
2. No Subgroup Analyses will be done.
3. The ITT Analysis will consider subjects with unilateral treatment. There will not be a per-Protocol analysis.
4. Due to very slow recruitment the study was prematurely terminated. Given the limited number of patients included in the database, compared to the plan the following data was not entered into the database and subsequently not analysed for the following endpoints:
  1. Geometry (roundness) of major lung airways as defined by the ratio of major versus minor diameter measured from 3 bronchoscopic still images prior and post procedure taken in the lobar airway of the carina leading to segmental airways or while in any segmental airways of the same lobe of the carina leading to sub-segmental airways)
  2. Static and dynamic pulmonary compliance measurement prior to and post treatment including closing volumes, closing capacity and small airways function
  3. Physical activity and energy expenditure measured over a period of a week using multi-axial accelerometer.
  4. heart ejection fraction, systemic blood pressure
  5. fat per mass
  6. Ventilation and perfusion single photon emission tomography (V/P SPECT) or Quantitative lung perfusion scintigraphy (LPS)
  7. Diaphragm position during exhalation (Comparison of diaphragm apex to rib landmarks using frontal HRCT)
  8. Lung density distribution (post CT image data processing and reconstruction)
  9. St. George's respiratory questionnaire (SGRQ)
  10. Chest X-Ray
5. Variables that were not planned to be documented according to protocol but have been documented:
  1. Pregnancy testing at visit 3 (3months post final Tx) and visit 4 (12 months post Tx1)

2. Static and dynamic pulmonary compliance at Baseline, visit 3 (3months post final Tx) and visit 4 (12 months post Tx1)
6. Due to the small number of patients there will not be any tables presented for secondary endpoints

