4.2 Number of Subjects

Thirty subjects will be enrolled into the study from each participating site. Subjects who completed only a unilateral treatment, for any reason will be replaced and not considered in the ITT analysis. Two sites will be recruiting subjects resulting in at least 60 enrolled and bilaterally treated subjects.

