9.2 Potential Benefits to the Subject

It is possible that a study subject will not receive any benefits from treatment with the Coil.

Potential benefits of the Coil treatment that may be realized by study subjects include overall reduction in number or severity of symptoms related to emphysema and improved quality of life.

Another potential benefit to subjects participating in the study is the ability to learn more about their emphysema based on the assessments that will be performed throughout the course of the study.

The results of this study may help other emphysema subjects to gain access to a device that may improve their quality of life and general health.

10 Study Monitoring

PneumRx and its designee(s) for Data Management and Biostatistics will be responsible for coordinating and conducting the handling of clinical study data.

Before acceptance of the clinical data, PneumRx and its assigned Clinical Monitor designee(s) will review the data entered on CRFs (case report forms) for completeness and adherence to the protocol based upon source documentation verification (SDV). Procedures to be followed and the data to be fully monitored to SDV will be described in detail in the Monitoring Plan. For example, all safety data and primary and secondary endpoint measures as defined by the protocol will be 100% monitored to SDV.

PneumRx and its designee(s) will qualify investigative study sites to review the adequacy of the subject population, facilities, equipment and resource needs of the study, and to familiarize the investigator with the study protocol.

At the time of enrollment, PneumRx and its designee(s) will meet with the investigator to ensure that subjects will be properly selected and enrolled, that the methods described in the study protocol are thoroughly understood and that the method(s) surrounding clinical data collection and capture are understood.

Assigned Clinical Monitors of PneumRx will visit the clinical site(s) periodically during the course of the study to perform SDV and perform device reconciliation. The Investigator and Institution must guarantee direct access to associated medical records by designated monitors and appropriate regulatory authorities.

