### 1.2 Study Design

This CLN0017 Study is a prospective, multicenter, open label, single-arm study. The objective of this post-marketing study is to advance the understanding of mechanism of action of the CE marked RePneu Coil by observing changes in lung physiology and cardiac performance in patients with emphysema treated with the RePneu Coils, when used as intended.

Investigators will have been trained and/or re-trained in the proper use and operation of the RePneu System, and will have performed several commercial procedures prior to initiation of any treatment.

Subjects must meet all of the following inclusion criteria to be entered into the study:

1. Adult subjects diagnosed with emphysematous type of COPD.
2. CT scan indicates bilateral emphysema, with sufficient lung parenchyma for coil deployment (based on PneumRx CT scoring) criteria.
3. Subject has post-bronchodilator FEV1  $\leq 45\%$  predicted.
4. Subject has Total Lung Capacity  $> 100\%$  predicted.
5. Subject has residual volume (RV)  $\geq 175\%$  predicted.
6. Subject has marked dyspnea scoring  $\geq 2$  on mMRC scale of 0-4.
7. Subject read, understood and signed the Informed Consent form.
8. Subject has received Pneumococcal and Influenza vaccinations consistent with local recommendations and/or policy

Subjects will be excluded from the study if any of the following conditions apply:

1. Subject has co-morbidities that may significantly reduce subject's ability to improve exercise capacity (e.g. severe arthritis, planned knee surgery) or baseline limitation not due to dyspnea.
2. Subject has a change in FEV1 >20% (or, for subjects with pre-bronchodilator FEV1 below 1 L, a change of > 200 mL) post-bronchodilator unless investigator can confirm by other means that subject does not have asthma.
3. Subject has severe gas exchange abnormalities as defined by:
  - a) a. PaCO2 >55 mm Hg
  - b) b. PaO2 <45 mm Hg on room air (High altitude criterion: PaO2 <30 mm Hg)
4. Subject has severe pulmonary hypertension defined by right ventricular systolic pressure >50 mm Hg via right heart catheterization and/or echocardiogram.
5. Subject has evidence of other severe disease (such as, but not limited to, lung cancer or renal failure), which in the judgment of the investigator may compromise survival of the subject for the duration of the study.
6. Subject is pregnant or lactating, or plans to become pregnant within the study timeframe.

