### 5.3.2 Demographics and vital signs

A table summarizing the following demographics parameters and vital signs will be presented for the final analyses:

- age at Baseline Visit (continuous)
- gender (male, female) (categorical)
- ethnicity (Hispanic or Latino, not Hispanic or Latino) (categorical)
- race (American Indian or Alaska Native, Black or African American, Asian, White, Native Hawaiian or Other Pacific Islander, other) (categorical)
- Body Mass Index (continuous)
- height (continuous)

- weight (continuous)
- Systolic blood pressure (continuous)
- Diastolic blood pressure (continuous)
- Heart Rate (continuous)
- Temperature (continuous)
- SpO2 (continuous)

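### Few patients is a reason to list without tests, not to leave out ejection fraction, blood pressure and SGRQ; heart rate becomes the only named cardiac measure left

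*SAP*

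**What the plan says.** The SAP repeats the protocol's objective unchanged in sections 1.2 and 1.3: to advance understanding of the mechanism of action "by observing changes in lung physiology and cardiac performance in patients with emphysema treated with the RePneu Coils".

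Protocol section 3 names three cardiovascular measures as secondary endpoints: heart rate, ejection fraction and systemic blood pressure. SGRQ is a separate secondary endpoint. Protocol Table 3 schedules SGRQ and echocardiogram at baseline and at the two main follow-up visits, the same three occasions as the 6-minute walk test. It schedules vital signs at every visit.

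SAP section 4 item 4 reports early termination for slow recruitment. Citing the limited number of patients, it says that "compared to the plan the following data was not entered into the database and subsequently not analysed for the following endpoints". Item 4.4 reads "heart ejection fraction, systemic blood pressure" and item 4.9 is SGRQ. SAP 1.3 carries the same list except for chest X-ray.

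SAP 5.6 keeps an effectiveness listing of 6MWT, FEV1, RV, RV/TLC, DLCO, mMRC, heart rate and body composition including BMI. Section 4 item 6 and section 5.6.2 restrict the secondary endpoints to per-patient listing because of the small sample.

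On data handling, protocol section 10 says that "all safety data and primary and secondary endpoint measures as defined by the protocol will be 100% monitored to SDV". Protocol section 12 requires everything generated by the subject evaluations to be transferred to the CRFs.

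**The concern.** The reason given does not lead to the decision taken. Few patients means little power and unstable summaries, which argues against tests and tables. It does not argue against recording a value that a subject has already provided. The SAP also does not explain why 6MWT and mMRC were entered when SGRQ, due at the same visits, was not.

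Two things are at stake. First, the study claims to observe cardiac performance, and what remains would be resting heart rate. Second, the set of reported endpoints was fixed in 2018, after termination of an open-label single-arm study, with a justification that does not discriminate between what was kept and what was cut. That leaves a selective-reporting question which the final report could not answer.

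**Working it through.** **1. Planned size.** The protocol (4.2) plans 30 subjects at each of two sites: "Two sites will be recruiting subjects resulting in at least 60 enrolled and bilaterally treated subjects". 30 × 2 = 60, which reproduces. The documents give no power calculation, and the actual number enrolled is not stated, only that it is below plan (SAP 1.2).

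**2. What is lost.** Protocol section 3 lists 2 + 9 + 3 = 14 secondary bullets. Set against SAP section 4 item 4 and SAP 5.6:

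| Status | Endpoints | Count |
|---|---|---|
| Dropped entirely | airway geometry, compliance, physical activity, SGRQ, V/P SPECT or LPS, diaphragm position, lung density | 7 |
| Cut down | cardiovascular (loses ejection fraction and blood pressure), body composition (loses fat mass) | 2 |
| Kept | FEV1, RV, RV/TLC, DLCO, mMRC | 5 |

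7 + 2 + 5 = 14.

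**3. Effect on each half of the objective.** Cardiac: 3 named measures − 2 dropped = 1 left, heart rate. Lung physiology: FEV1, RV, RV/TLC and DLCO remain, each with change from baseline. SGRQ is a questionnaire and belongs to neither half.

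**4. Does small N explain non-entry?** Ejection fraction and SGRQ total are each due at 3 visits, so values to enter per endpoint = 3 × N.

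| N | Values per endpoint |
|---|---|
| 5 (assumed) | 15 |
| 10 (assumed) | 30 |
| 20 (assumed) | 60 |
| 30 (assumed) | 90 |
| 60 (planned) | 180 |

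The work shrinks in proportion to N, so a low N makes entry easier than the plan had foreseen.

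**5. Blood pressure.** Item 4.4 lists systemic blood pressure as not entered. SAP 5.3.2 tabulates systolic and diastolic pressure at baseline, in the same vital-signs list as heart rate. Heart rate is then carried into the 5.6 listing and blood pressure is not. No reason is given for treating the two differently.

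**6. Compliance.** Item 4.2 lists static and dynamic compliance as not entered. Item 5.2 of the same section says it was documented at baseline, visit 3 and visit 4. SAP 1.3 adds an esophageal-balloon compliance measure (item 10) as a secondary endpoint at the follow-up visits. The 5.6 listing contains no compliance measure.

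**7. SGRQ.** Every row of protocol Table 1 reports an SGRQ change, from −6.1 to −15 points. A reader setting this study beside that background would have nothing to put in the column.

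**The case against.** The strongest reply is that the SAP is open about the cut: it appears in section 1.3 and again in section 4, and the SAP version for the final analysis must be final before database lock (SAP 1.1). Not entered may also mean not collected, or collected too patchily to be worth entering. The eCRF is not available here, so it is unknown whether fields for ejection fraction or SGRQ exist, and late entry could bring form changes, queries and source verification. All of this stands. It is why the request is limited to cases where source data exist.

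Both inconsistencies have a possible innocent reading. Item 4.4 concerns an endpoint, which is change at follow-up, so baseline pressure could be in the database while follow-up pressure is not. The SAP's own visit schedule cannot be read in the available text, so this cannot be settled. Item 4.2 repeats the wording of the endpoint measured before and after each procedure, whereas item 5.2 concerns scheduled visits. If that distinction is meant, the SAP does not say so, and the visit-based compliance values are still missing from 5.6 without explanation.

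It is also fair that Table 1 is background and neither document plans a comparison with it, that the listing adds no inference, and that the primary endpoint is untouched.

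A reader might infer that results were known and guided the choice. The documents do not support that. No section says anyone had seen SGRQ or echocardiogram results, and the list mixes imaging, accelerometry, body composition and chest X-ray with no visible pattern.

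**Conclusion.** The point holds in limited form. The stated reason supports listing without tests but not omission. Seven of 14 secondary bullets are lost and two reduced. Two of three named cardiac measures go, so the cardiac half of the objective is in effect unanswered.

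A reader might go further and say that the study can no longer meet its objective at all. That is too strong: four lung-function measures are still listed with change from baseline, and the loss of SGRQ does not bear on the objective as worded. Nor can entry be called trivial when the actual N is not stated. For endpoints that need image processing, the effort could be considerable.

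On selective reporting, the supportable statement is that the reason given does not rule it out. The blood pressure and compliance statements need reconciling and are not proof of error.

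The conclusion assumes that at least some source data exist for the omitted measures. The documents directly support this only for baseline blood pressure, which SAP 5.3.2 plans to tabulate, and for compliance, which item 5.2 calls documented.

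**What to change.** 1. Reconcile section 4 item 4.4 with 5.3.2 by stating at which visits blood pressure is in the database. Reconcile item 4.2 with item 5.2 by stating which compliance measurements were entered and which were not.
2. Add blood pressure and the documented compliance values to Listing 16.6, per patient, without tests, as for the other secondary endpoints.
3. Enter ejection fraction and SGRQ total where source data exist for baseline and the two follow-up visits, and add them to the same listing.
4. For every prespecified endpoint still omitted, state how many patients have source data. If a measure was never collected, the count will show it.

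Cost: steps 1 and 2 are text edits and a few listing columns, provided the values are already in the database. Step 3 needs some late entry and checking, about 3 × N values per endpoint, or 15 to 90 if N lies between 5 and 30 (an assumption). It could cost more if the eCRF lacks the fields. Step 4 needs a count from the sites. The image-processing endpoints need no new work beyond that count.

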## 5 PLANNED ANALYSES

### 5.1 Overview of safety variables

For data cleaning and data quality purposes an overview of safety variables will be created in the form of an Excel listing monthly.

### 5.2 Study Patients

A listing with general information on the study patients will be provided, including:

- Study site
- Informed consent date
- Termination date and reason for discontinuation (if applicable)
- Death (yes/no) and, if yes, death date and whether death is emphysema related or unrelated to emphysema

#### 5.2.1 Patient Disposition

The patient accountability will be assessed for the final analysis by showing the number of patients at the following times:

- Patients enrolled
- Patients included in analysis sets
- Patients received the first procedure
- Patients received the second procedure
- Patients at 3-Months Follow-Up
- Patients at 12-Months Follow-Up
- Patients completing the study

The Patients who permanently discontinued the study before the end of the study will be presented in a listing, including the reason for discontinuation. A flow chart will be created on request.

## 5.2.2 Protocol Deviation

A listing with information on protocol deviations will be provided, including:

- Inclusion/Exclusion Criteria not met
- Lost-to-follow-up
- Unilateral treatment
- 1 month post treatment 1 Visit not done
- 1 month post treatment 2 Visit not done
- 3 months post final treatment Visit not done
- 12 months post treatment 1 Visit not done

## 5.3 Baseline Data

Continuous data will be summarized using descriptive statistics (mean, SD, min, median, max). Additionally, the number of patients included in the patient set (N), number of patients contributing to the analysis (n) and the number of patients not included in the analysis due to missing data (missing) will be displayed.

Categorical variables will be displayed as frequencies (p/n) and percentages (i.e. absolute and relative frequencies). Unless otherwise noted, percentages will be based on the patients available for analysis (non-missing). The number of patients with missing data will be also be summarized.

All baseline analyses will be based on the Intention-to-treat Set (ITT).

Furthermore, all of the baseline data mentioned in the following subsections 5.3.1-5.3.6 including text specifications will be listed.

### 5.3.1 Enrollment by site

A table showing the number and percentage of enrolled patients by site will be provided for the final analyses.

### 5.3.2 Demographics and vital signs

A table summarizing the following demographics parameters and vital signs will be presented for the final analyses:

- age at Baseline Visit (continuous)
- gender (male, female) (categorical)
- ethnicity (Hispanic or Latino, not Hispanic or Latino) (categorical)
- race (American Indian or Alaska Native, Black or African American, Asian, White, Native Hawaiian or Other Pacific Islander, other) (categorical)
- Body Mass Index (continuous)
- height (continuous)

- weight (continuous)
- Systolic blood pressure (continuous)
- Diastolic blood pressure (continuous)
- Heart Rate (continuous)
- Temperature (continuous)
- SpO2 (continuous)

### **5.3.3 Baseline Characteristics**

A table showing the following baseline characteristics will be presented for the final analyses:

- FVC in L (continuous)
- FVC % predicted (continuous)
- FEV1 in L (continuous)
- FEV1 % predicted (continuous)
- (FEV1 in L/FVC in L) in % (continuous)
- RV in L (continuous)
- RV % predicted (continuous)
- 6MWT in m (continuous)
- mMRC (0, 1, 2, 3, 4) (categorical)
- mMRC (continuous)

### **5.3.4 Medical History**

A table summarising the medical history (comorbidities) will be created by assessing the parameters from the eCRF (in dataset *mh*) for final analyses

### **5.3.5 History and Characterization of Emphysema**

A table will be created to show the history and characterization of the emphysema for final analyses by the following:

- How many YEARS has the subject been diagnosed with emphysema
- Number of unscheduled PHYSICIAN visits
- Number of EMERGENCY ROOM visits
- Number of HOSPITALIZATIONS

### 5.3.6 Treatment of Emphysema

A table summarising the treatment of emphysema will be created by assessing the parameters from the eCRF (in dataset *emph treat*) for final analyses.

## 5.4 Procedural analyses

For the following sections tables will be created to describe the RePneu® procedures.

Additionally a listing will be prepared to show

- the coils per procedure,
- the total coils implanted,
- the total bronchoscopy time and the total fluoroscopy time,
- the post-procedural hospital stays and
- the type of medication prescribed in preparation for the procedure as well as the corresponding name of the medication, the medication start and stop date and the total daily dosage (will only be done for final analyses)

### 5.4.1 Number of Devices implanted

A table summarizing treatment lobes and coils implanted will be presented for all procedures and separately for each procedure:

- Coils Per Procedure (continuous)
- Total Coils Implanted (upper right lobe, upper left lobe, lower right lobe, lower left lobe, middle right lobe) (categorical)

### 5.4.2 Procedure Time

A table showing the total bronchoscopy time and the total fluoroscopy time in minutes (continuous) will be created for all procedures and separately for each procedure.

### 5.4.3 Post-Procedure Hospital Stay

A table summarizing the post-procedure hospital stay in days (continuous) will be prepared for all procedures and separately for each procedure.

The post-procedural hospital stay is calculated as

*post-procedural hospital stay* = *discharge date (exdisdtu)* – *admission date (exprdt)* in the dataset *bcproc*.

## 5.5 Safety analyses

A listing for adverse events will be provided for the final analyses, consisting of the following information of each AE:

- Site
- Subject ID
- AE Term
- SOC
- PT
- AE start date
- AE stop date
- Duration of AE
- Procedure dates
- Days post procedures
- Seriousness, including the primary reason for classification as serious
- Relation to device
- Relation to procedure
- Event outcome

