4.6 Statistical analysis

The endpoints will be analyzed with a paired t-test, which will compare baseline to 4-month post final treatment and 12-months post first treatment follow-up values. A p-value of <0.05 will be considered statistically significant. Parametric descriptive statistics will be used to summarize data for secondary effectiveness variables. Adverse events will be categorized into medically relevant categories and presented as frequency counts and percentages.

Intention to Treat (ITT) and Per-protocol analyses will be performed as well as a site-specific subgroup analysis.

Other subgroup analyses will include:

- upper vs. lower lobe treatments
- multi-variate analysis of baseline characteristics, adverse events, and various CT and other imaging characteristics

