6.7 Unscheduled Visits

It is expected that some subjects may present during the follow-up period with complaints (e.g., COPD exacerbation). These visits and the findings should all be recorded on the appropriate CRFs. Notify the Sponsor if an unscheduled visit occurs.

7 Management of Adverse Events (AEs) and Serious Adverse Events (SAEs)

An adverse event (AE) is any untoward medical occurrence in a study subject. This may include symptom(s), illness, clinically significant abnormal laboratory value or change in value, or worsening in a subject during a clinical study.

It is the responsibility of the investigator to report when he/she becomes aware that an adverse event has occurred. AE information will be collected throughout the study. Adverse events will be recorded on the CRF by the investigator or authorized designee. Event, date of onset, severity, duration, and relationship to the procedure/device will be recorded. All adverse events will be followed until they are adequately resolved or stabilized, or for 1 month following study completion or termination, whichever comes first.

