7.3 Severity of AEs and SAEs

The following general definitions for rating severity should be used for this study:

1. **Mild:** Awareness of signs or symptoms, but easily tolerated and transient; causing no loss of time from normal activities; symptoms would not require medication or a medical treatment; signs and symptoms are transient.
2. **Moderate:** Marked symptoms and discomfort severe enough to cause moderate interference with the subject's usual activities. Symptomatic treatment is possible.
3. **Severe:** Incapacitating with inability to do work or usual activities; signs and symptoms may be of systemic nature or require medical intervention and/or treatment. Hospitalization may be required or prolonged.

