### **5.5.1 Adverse events**

A table showing the number and percentage of events as well as the number and percentage of patients with at least one event will be provided for any AE and for AE according to SOC and PT.

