### **5.5.2 Serious adverse events**

A table showing the number and percentage of events as well as the number and percentage of patients with at least one event will be provided for any serious AE and for serious AE according to SOC and PT.

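### The SAP's itemised adverse event listing and tables leave out the severity grade that the protocol requires for each event

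*SAP*

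**What the plan says.** The opening text of protocol section 7 names what is recorded for an AE: "Event, date of onset, severity, duration, and relationship to the procedure/device will be recorded". The synopsis says the same. Section 7.3 introduces a three-grade scale with "The following general definitions for rating severity should be used for this study" and defines mild, moderate and severe.

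For analysis, protocol section 4.6 says only this: "Adverse events will be categorized into medically relevant categories and presented as frequency counts and percentages".

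SAP section 5.5 introduces the AE listing with "A listing for adverse events will be provided for the final analyses, consisting of the following information of each AE" and then gives a closed list of fields. The nearest field to severity is "Seriousness, including the primary reason for classification as serious". Section 5.5.1 describes a table of events and patients that "will be provided for any AE and for AE according to SOC and PT". Section 5.5.2 does the same for serious events, and section 5.5.3 for device- and procedure-related events. Appendix I numbers these tables 14.6.1, 14.6.2 and 14.6.3 and contains no table by severity.

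SAP section 4 sets out the changes from the protocol, including the data that were not entered into the database. AE severity is not mentioned there.

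**The concern.** The protocol makes severity a required AE item and gives sites a scale for grading it. A programmer who follows the SAP as written would produce a listing and three tables without it, and a reader of the SAP would not learn that it had been left out.

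Seriousness does not fill the gap, because the protocol defines the two by different criteria. A severe event that is not serious would appear in the listing and in Table 14.6.1 without its grade, under the same SOC and PT as mild events of the same kind. This is a single-arm study that stopped early, and its secondary effectiveness endpoints are reduced to a listing (SAP section 5.6.2). The event-level AE listing is therefore an important part of what can be reported. Without the grade, the itemised outputs cannot support a statement on how severe the device- and procedure-related events were.

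**Working it through.** No plan figure needs reproducing. The check is a comparison of fields.

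**1. Protocol AE items against the SAP section 5.5 listing**

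| Item named in protocol section 7 | In the SAP 5.5 listing? |
|---|---|
| Event | Yes (AE term, SOC, PT) |
| Date of onset | Yes (start date) |
| Severity | No |
| Duration | Yes (duration, and stop date) |
| Relationship to procedure/device | Yes (two separate fields) |

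Four of the five items are carried. Severity is the only one missing.

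**2. Count of listing fields.** Site, subject ID, AE term, SOC and PT make 5. Start date, stop date, duration, procedure dates and days post procedures make 5 more. Seriousness with its reason, relation to device, relation to procedure and outcome make 4. The total is 5 + 5 + 4 = 14, and 0 of 14 is severity.

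**3. Tables.** Sections 5.5.1 to 5.5.3 describe three tables, each showing an overall line and then SOC and PT. None shows severity: 0 of 3.

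**4. Does seriousness stand in for severity?** Protocol section 7.3 defines severe as "Incapacitating with inability to do work or usual activities; signs and symptoms may be of systemic nature or require medical intervention and/or treatment", and adds that hospital admission may be needed or prolonged. Admission is thus a possible feature of a severe event and not a condition for the grade. Section 7.1 gives six criteria for a serious event: death, threat to life, inpatient admission or its prolongation, persistent or significant disability or incapacity, congenital anomaly or birth defect, and intervention to prevent permanent impairment or damage. An event that is incapacitating for a time, and is treated without admission, can be graded severe and meet none of the six. The serious-event table, which "will be provided for any serious AE and for serious AE according to SOC and PT", would not include it. Table 14.6.1 would include it, without its grade.

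**5. Is the omission declared?** SAP section 4 goes down to the level of chest X-ray and pregnancy testing. AE severity appears neither as a change nor among the data not entered.

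**The case against.** The strongest reply is that no promised analysis has been lost. The protocol's analysis text asks for AE counts and percentages by category, and the SAP delivers them. Sections 7 and 7.3 govern recording and grading, not tabulation. This stands: a reader might infer that the SAP dropped a planned severity analysis, but the documents do not support that. What is left out is a required data item, and the silence of SAP section 4 should be read in that light.

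Four other strong readings also go too far.

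- *That a severe event managed outside hospital is not serious.* Admission is one of six criteria, and an incapacitating event may meet another. The gap covers only severe events that meet none of the six.
- *That severity would appear in no output at all.* Appendix I has a listing titled Overview of safety variables, and SAP sections 2.2 and 5.1 plan a monthly Excel overview for data cleaning and quality. The fields of neither are itemised under those names. They might carry severity, but nothing says that they do.
- *That severe non-serious events could not be told from mild ones in any way.* The listing gives duration, outcome, relatedness and timing for each event. These describe the event but do not give its grade.
- *That the grades are already collected and verified.* The SAP was built on an annotated eCRF that is not among the documents. Because severity is not listed as data not entered, it was probably captured, but that is an inference. Protocol section 10 plans full source verification of safety data, which does not show that it was done.

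It is also fair to say that severity rows by PT would be sparse in a small sample, and that SAP section 3.3.2 already allows minor table changes. The first point limits the fix. The second allows it but does not commit anyone to it.

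**Conclusion.** The point holds. A safety variable that the protocol requires for each AE is missing from every itemised AE output in the SAP (0 of 14 listing fields, 0 of 3 tables), while the other four AE items are carried and the omission is not declared. The consequence is limited: the itemised outputs would not show the grade of severe, non-serious events. The documents give no basis for saying how many such events there would be.

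The primary endpoint, the analysis set, the selection of events for the serious-event table and the deaths listing are unaffected. The conclusion rests on reading the section 5.5 field list as complete, which is how its introduction presents it. The fix also assumes that the eCRF captured severity.

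**What to change.** Add a column, Severity (mild/moderate/severe), to the AE listing in SAP section 5.5, using the grades in protocol section 7.3. Add one overall row to each of Tables 14.6.1 and 14.6.3, giving the number of severe events and the number of patients with at least one severe AE. Do not break severity down by PT.

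If the eCRF did not capture severity, state that in SAP section 4 as a departure from the protocol.

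The cost is the programming of one listing column and two table rows.
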